Enrolment in the study will be confirmed by completing the Enrolment form on the electronic case report form (eCRF). Information collected for screening failures include date of informed consent, inclusion/exclusion criteria, and serious adverse events (SAE) where relevant.

[figure not shown]
Treatment phase

Patients will start study treatment on Day 1 with everolimus 10 mg daily p.o. (either 2 x 5 mg or 1 x 10 mg tablets) in combination with exemestane 25 mg daily p.o. (25 mg tablets). Dose adjustment (reduction or interruption) will be allowed according to safety findings and dose adjustment guidelines. Study treatment will continue until disease progression, unacceptable toxicity, death, consent withdrawal or any other reason. Further treatment after progression will be at the investigator's discretion.

During the study, visits will be performed at Screening, Baseline/Treatment Day 1 (Treatment start), Week 4 (\pm 1 week), Week 10 (\pm 2 weeks), and then every 10-weekly (\pm 2 weeks) till end of treatment.

Tumor evaluations through CT scan/MRI will be performed for Screening, at Week 10, and 10 weekly thereafter. All radiological evaluations and laboratory assessments will be performed locally, at the center level. Patients will be followed up for safety for 30 days (\pm 2 days) after the last dose of everolimus. AEs/SAEs with a suspected causality to the study drug must be reported beyond this 30 days safety interval.

Figure 4-1 Study design

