7.1 Study flow and visits schedule

[Table 7-1](#) lists all study assessments by visit. All data obtained from these assessments must be supported in the patient's source documentation. All assessments will be captured in the CRF, with the only exception of safety laboratory tests and ECG, which will remain only in the patient's source documents.

Tests, procedures and visits should occur on schedule as far as possible.

[figure not shown]
[figure not shown]
[figure not shown]

Table 7-1 Schedule of assessments

[figure not shown]
	Screening Day -21 to -1	Baseline Day 1	Week 4 ± 1 week	Week 10 ± 2 weeks	Week 20 ± 2 weeks	Week 30 ± 2 weeks	Week 40 ± 2 weeks	Week 50 ± 2 weeks/ EOT	Following visits (each 10 ± 2 weeks)	EOT	Follow-up EOT + 30 days (± 2 days)
Visit N°	1	2	3	4	5	6	7	8	N	EOT	F-up
Informed consent	X										
Demographics	X										
Eligibility criteria	X	X									
Medical history, current medical conditions	X										
Diagnosis and extent of breast cancer	X										
Prior antineoplastic therapies	X										
Height, weight	X										
Physical examination	X	X	X	X	X	X	X	X	X	X	
Vital signs, ECOG status	X	X	X	X	X	X	X	X	X	X	
Prior medications	X										
Concomitant medications	X	X	X	X	X	X	X	X	X	X	X
Adverse events	X	X	X	X	X	X	X	X	X	X	X
Study drugs dispensation		X	X	X	X	X	X	X	X		
CT scan/MRI chest, abdomen,	X			X	X	X	X	X	X	X	

	Screening Day -21 to -1	Baseline Day 1	Week 4 ± 1 week	Week 10 ± 2 weeks	Week 20 ± 2 weeks	Week 30 ± 2 weeks	Week 40 ± 2 weeks	Week 50 ± 2 weeks/ EOT	Following visits (each 10 ± 2 weeks)	EOT	Follow-up EOT + 30 days (± 2 days)
Visit N°	1	2	3	4	5	6	7	8	N	EOT	F-up
pelvis (1)											
Brain CT scan or MRI (2)	X	As clinically indicated									
Bone scan/ X-ray (3)	X	If bone metastases are present at baseline, a bone scan or skeletal survey is required every 10 weeks. If bone metastases are not identified at baseline, bone scans will be performed as clinically indicated									
Bone CT/MRI (3)	X	If bone metastases are present at baseline, a bone scan or skeletal survey is required every 10 weeks. If bone metastases are not identified at baseline, bone CT/MRI will be performed only to confirm potential findings identified by bone scans/X-rays.									
Hematology, chemistry, lipid profile (5)	X	X	X	X	X	X	X	X	X	X	
Hepatitis B viral load and markers	X	Monitor approximately every 3-6 weeks when required.									
Hepatitis C viral load and markers	X	Monitor approximately every 6 weeks when required.									

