10.2 General statistical methods

The data will be summarized with respect to demographic and baseline characteristics, efficacy observations and measurements, and safety observations and measurements. Primary efficacy and safety/tolerability analysis will be conducted at 15 months of median follow up time, i.e. at approximately two times the median PFS reported in the BOLERO-2 study (Baselga et al. 2012; Yardley D. et al. 2014). Categorical variables will be summarized by absolute and relative frequencies. Continuous variables will be summarized by descriptive statistics (number of valid and missing observations, mean, standard deviation, median, minimum, and maximum).

Time to event data including rates of affected patients will be assessed using the Kaplan-Meier method. Two-sided 95% confidence intervals will be provided for the main statistical estimators.

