10.6.1.3 Progression-free survival

Progression-free survival (PFS) is the time from date of start of treatment to the date of event defined as the first documented progression or death due to any cause. If a patient has not had an event, progression-free survival is censored at the date of last adequate tumor assessment.

Disease progression will be assessed using the local (treating center's radiologist's) investigator's tumor assessment. PFS will be summarized using the Kaplan-Meier method. Percentiles (25%, median, 75%) of the event time distribution will be presented along with their two-sided 95% confidence interval. The Kaplan-Meier curve will be displayed graphically.

[figure not shown]

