14.1.24 Definition of start and end dates for time to event variables

Assessment date

For each assessment (i.e. evaluation number), the **assessment date** is calculated as the latest of all measurement dates (e.g. X-ray, CT-scan) if the overall lesion response at that assessment is CR/PR/SD/UNK. Otherwise - if overall lesion response is progression – the assessment date is calculated as the earliest date of all measurement dates at that evaluation number.

Start dates

[figure not shown]
For all “time to event” variables, other than duration of response, the randomization/ date of treatment start will be used as the start date.

For the calculation of duration of response the following start date should be used:

- Date of first documented response is the assessment date of the first overall lesion response of CR (for duration of overall complete response) or CR / PR (for duration of overall response) respectively, when this status is later confirmed.

End dates

The end dates which are used to calculate ‘time to event’ variables are defined as follows:

- Date of death (during treatment as recorded on the treatment completion page or during follow-up as recorded on the study evaluation completion page or the survival follow-up page).
- Date of progression is the first assessment date at which the overall lesion response was recorded as progressive disease.
- Date of last adequate tumor assessment is the date the last tumor assessment with overall lesion response of CR, PR or SD which was made before an event or a censoring reason occurred. In this case the last tumor evaluation date at that assessment is used. If no postbaseline assessments are available (before an event or a censoring reason occurred) the date of randomization/start of treatment is used.
- Date of next scheduled assessment is the date of the last adequate tumor assessment plus the protocol specified time interval for assessments. This date may be used if back-dating is considered when the event occurred beyond the acceptable time window for the next tumor assessment as per protocol (see [Section 14.1.25](#)).

Example (if protocol defined schedule of assessments is 3 months): tumor assessments at baseline - 3 months - 6 months - missing - missing - PD. Date of next scheduled assessment would then correspond to 9 months.

- Date of discontinuation is the date of the end of treatment visit.

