Asian: Indonesia, India, Vietnam, Turkey, South Korea, Thailand, Malaysia, Taiwan or Jordan.

Non-Asian: Australia, Morocco, South Africa or Tunisia.

^a Duration of overall response: Time from the date of the first of two documented CR or PR for at least 4 weeks or one documented CR or PR where confirmation not required to the date of first documented disease progression or death due to underlying cancer.

^b Duration of clinical benefit: Time from the date of the first of CR (any duration), PR (any duration) or SD (with duration of 24 weeks) to the date of first documented disease progression or death due to underlying cancer.

^c Duration of stable disease: Time from the start of treatment date to date of first documented disease progression or death due to underlying cancer.

^d For effectiveness evaluation (progression-free survival), patients without progression or death are right-censored at the date of their last tumor response evaluation.

^e Time from the date of last tumor assessment to date of end of study visit. In case of end of study visit date missing, date of last follow-up visit or date of end of treatment, whichever occurs later, will be used.

Table 8.2.2 Duration of Clinical Response Overall and in Asian Subgroup - Per Protocol Set

This table will be created using the same layout as Table 8.2.1.

Table 8.3.1 Progression-Free Survival Overall and in Asian Subgroup - Full Analysis Set

	Asian (N=xx)		Non-Asian (N=xx)		Total (N=xxx)	
	No. of patients at risk	Event-free probability estimates (%) ^c	No. of patients at risk	Event-free probability estimates (%) ^c	No. of patients at risk	Event-free probability estimates (%) ^c
Progression-free survival (PFS) time ^a						
Week 4	xxx	x.x	xxx	x.x	xxx	x.x
Week 10	xxx	x.x	xxx	x.x	xxx	x.x
Week 20	xxx	x.x	xxx	x.x	xxx	x.x
Week 30	xxx	x.x	xxx	x.x	xxx	x.x
Week 40	xxx	x.x	xxx	x.x	xxx	x.x
Week 50	xxx	x.x	xxx	x.x	xxx	x.x
Etc. (as appropriate)						
Total number of events, n (%)	xx (xx.x)		xx (xx.x)		xx (xx.x)	
Progression, n (%)	xx (xx.x)		xx (xx.x)		xx (xx.x)	
Death, n (%)	xx (xx.x)		xx (xx.x)		xx (xx.x)	
Total number of censored, n (%)	xx (xx.x)		xx (xx.x)		xx (xx.x)	
Percentiles (95%CI) (weeks) ^b						
25 th percentile	xx.x (xx.x, xx.x)		xx.x (xx.x, xx.x)		xx.x (xx.x, xx.x)	
Median	xx.x (xx.x, xx.x)		xx.x (xx.x, xx.x)		xx.x (xx.x, xx.x)	
75 th percentile	xx.x (xx.x, xx.x)		xx.x (xx.x, xx.x)		xx.x (xx.x, xx.x)	

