Asian: Indonesia, India, Vietnam, Turkey, South Korea, Thailand, Malaysia, Taiwan or Jordan.

Non-Asian: Australia, Morocco, South Africa or Tunisia.

^a PFS is time from date of start of treatment to date of disease progression or death due to any cause, whichever occurs first.

^b Percentiles with 95% CIs are calculated from PROC LIFETEST output using method of Brookmeyer and Crowley (1982).

^c Event-free probability estimate is the estimated probability that a patient will remain event-free up to the specified time point. Event-free probability estimates are obtained from the Kaplan-Meier survival estimates.

Table 8.3.2 Progression-Free Survival Overall and in Asian Subgroup - Per Protocol Set

Table 8.3.3 Progression-Free Survival Overall and in Asian Subgroup – Sensitivity Analysis

These tables will be created using the same layout as Table 8.3.1.

Table 8.3.4 Distribution of Time to Progression-Free Survival Overall and in Asian Subgroup by Analysis Set

This table will be created using the same layout as Table 7.3.3.

[figure not shown]

Table 10.1.1 Vital Signs: Observed and Change from Baseline - Safety Set

Visit	Statistic	Body Temperature (°C)	Heart Rate (bpm)	Sitting Systolic Blood Pressure (mmHg)	Sitting Diastolic Blood Pressure (mmHg)
Total (N=xxx)					
Baseline (BL)	n	xx	xx	xx	xx
	Mean (SD)	xx (xx.x)	xx (xx.x)	xx (xx.x)	xx (xx.x)
	Median	xx	xx	xx	xx
	Min, Max	xx.x, xx.x	xx.x, xx.x	xx.x, xx.x	xx.x, xx.x
Week 4	n	xx	xx	xx	xx
	Mean (SD)	xx (xx.x)	xx (xx.x)	xx (xx.x)	xx (xx.x)
	Median	xx	xx	xx	xx
	Min, Max	xx.x, xx.x	xx.x, xx.x	xx.x, xx.x	xx.x, xx.x
Week 4 Change from BL	n	xx	xx	xx	xx
	Mean (SD)	xx (xx.x)	xx (xx.x)	xx (xx.x)	xx (xx.x)
	Median	xx	xx	xx	xx
	Min, Max	xx.x, xx.x	xx.x, xx.x	xx.x, xx.x	xx.x, xx.x
Week 10	n	xx	xx	xx	xx
	Mean (SD)	xx (xx.x)	xx (xx.x)	xx (xx.x)	xx (xx.x)
	Median	xx	xx	xx	xx
	Min, Max	xx.x, xx.x	xx.x, xx.x	xx.x, xx.x	xx.x, xx.x
Week 10 Change from BL	n	xx	xx	xx	xx
	Mean (SD)	xx (xx.x)	xx (xx.x)	xx (xx.x)	xx (xx.x)
	Median	xx	xx	xx	xx
	Min, Max	xx.x, xx.x	xx.x, xx.x	xx.x, xx.x	xx.x, xx.x
Include Weeks 20, 30, 40, 50, etc.	:	:	:	:	:
End of Treatment (EOT)	n	xx	xx	xx	xx
	Mean (SD)	xx (xx.x)	xx (xx.x)	xx (xx.x)	xx (xx.x)
	Median	xx	xx	xx	xx
	Min, Max	xx.x, xx.x	xx.x, xx.x	xx.x, xx.x	xx.x, xx.x
EOT Change from BL	n	xx	xx	xx	xx
	Mean (SD)	xx (xx.x)	xx (xx.x)	xx (xx.x)	xx (xx.x)
	Median	xx	xx	xx	xx
	Min, Max	xx.x, xx.x	xx.x, xx.x	xx.x, xx.x	xx.x, xx.x

SD: Standard Deviation.

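### SAP Table 8.3.1 reads PFS rates at the centre of each ±2-week scan window and without confidence intervals, so the printed rates depend on scan punctuality and show no precision

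*SAP*

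**What the plan says.** **Endpoint.** Protocol section 10.6.1.3: "Progression-free survival (PFS) is the time from date of start of treatment to the date of event defined as the first documented progression or death". Appendix section 14.1.24 sets the date of a progression: "Date of progression is the first assessment date at which the overall lesion response was recorded as progressive disease". Protocol Table 3-1 lists the PFS rate, with ORR and CBR, as key secondary.

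**Scans.** Protocol section 4.1: "Tumor evaluations through CT scan/MRI will be performed for Screening, at Week 10, and 10 weekly thereafter". Table 7-1 gives the tolerance, for example "Week 10 ± 2 weeks". Week 4 is a visit without a scheduled scan. Scans outside the schedule also get a RECIST evaluation (Table 7-1, note 1), and a scan is mandated at end of treatment (Table 7-2).

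**Table.** The shell is titled "Table 8.3.1 Progression-Free Survival Overall and in Asian Subgroup - Full Analysis Set". Its rows are Weeks 4, 10, 20, 30, 40 and 50, with later weeks as appropriate. Each regional column gives the number at risk and "Event-free probability estimates", which footnote c explains: "Event-free probability estimate is the estimated probability that a patient will remain event-free up to the specified time point". Only the 25th, 50th and 75th percentiles have confidence intervals. Tables 8.3.2, 8.3.3 and S1 to S4.8.3.1 reuse the layout.

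**Precision.** Protocol section 10.2: "Two-sided 95% confidence intervals will be provided for the main statistical estimators". Section 10.6.1.3 names intervals for the PFS percentiles and is silent on the rates.

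**The concern.** A row labelled Week 10 invites the reader to take it as the result of the Week 10 scan. The Kaplan-Meier curve falls mostly inside the scan windows, and the table reads it halfway down each fall. A patient who has progressed and is scanned, within protocol, at week 11 counts as event-free at Week 10. The same patient scanned at week 9 counts as an event. Appendix section 14.1.33 adds one day to every duration, so even a scan exactly 70 days after treatment start is dated day 71, after the Week 10 reading.

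The Week 4 row precedes every scheduled on-treatment scan. It mainly reflects early deaths and unscheduled or early end-of-treatment scans, and nothing in the shell says so.

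These rows are the only time-specific PFS rates in the shells, and the main PFS tables set Asian beside Non-Asian patients. Without an interval, the reader cannot tell a regional difference from noise or from scan timing.

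**Working it through.** The plan states no PFS rate or precision target, so there is no planned figure to reproduce.

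**Inputs**
- Scans at 10k weeks, k = 1, 2, …, window ±2 weeks (protocol section 4.1, Table 7-1).
- Median PFS of the combination arm in the earlier phase III trial: 7.82 months at the final analysis, 6.93 at the interim (protocol section 1.2.1.2.2). 7.82 × 365.25/12/7 = 34.0 weeks.
- Assumptions: exponential time to underlying progression with that median; scan offsets uniform over the window; every event found at a scan; no other censoring. Using a documented-PFS median for underlying progression is itself an approximation.

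**Formula.** λ = ln 2/34.0 = 0.02038 per week and S(t) = exp(−λt). At week 10k, half the patients have had scan k, on average at week 10k − 1. For the other half the latest scan is the previous one, centred on week 10(k − 1). So, to a close approximation,

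reading at week 10k = ½·S(10k − 1) + ½·S(10(k − 1)).

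At week 10k + 2 everyone has had scan k, so the reading is close to S(10k).

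- Week 10: ½(0.832) + ½(1.000) = 91.6%, against S(10) = 81.6%.
- Week 50: ½(0.368) + ½(0.443) = 40.5%, against S(50) = 36.1%.

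A simulation of 400,000 patients under the same assumptions gives:

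| Scan | Read at nominal week | Read at window close | Underlying S at nominal week | Excess at nominal week (points) |
|---|---|---|---|---|
| Week 10 | 91.6% | 81.6% | 81.6% | 10.1 |
| Week 20 | 74.7% | 66.5% | 66.5% | 8.2 |
| Week 30 | 60.8% | 54.2% | 54.3% | 6.6 |
| Week 40 | 49.6% | 44.2% | 44.2% | 5.4 |
| Week 50 | 40.4% | 36.0% | 36.1% | 4.4 |

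The excess is taken before rounding. At Week 4 the same model prints 100% against S(4) = 92.2%, an excess of 7.8.

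**Other assumptions**
- 30% of events dated when they occur (deaths, unscheduled scans): the excess is multiplied by 0.7. Week 10: 0.7 × 10.1 ≈ 7.0. Week 50: 0.7 × 4.4 ≈ 3.
- Median 6.93 months: 11.2 points at Week 10, 4.4 at Week 50.
- All scans in the early half-window: 1.8 points at Week 10, 0.8 at Week 50.
- All scans in the late half-window: no scan precedes Week 10, so the reading is 100% and the excess 100 − 81.6 = 18.4. At Week 50 it is 7.3.
- Extremes for Weeks 10 to 50 over all runs: about 0.5 (early scans, 30% dated at occurrence) to 20.5 (late scans, 6.93-month median).

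**Interval width.** Half-width ≈ 1.96·√(S(1 − S)/N), ignoring censoring.
- N = 400: S = 0.816 gives ±3.8 points; S = 0.543 gives ±4.9.
- N = 100: ±7.6 and ±9.8.

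**The case against.** **The target.** PFS is defined by documented progression and dated at the assessment, and for that endpoint Kaplan-Meier at Week 10 is not biased. This stands. A reader might infer that the rates are simply wrong by 4 to 10 points. The documents do not support that: the excess is relative to underlying progression, or to status after the window's scan, and its size depends on the assumptions above.

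**Other event sources.** Deaths count as events, and unscheduled and end-of-treatment scans count too. This also stands. It reduces the excess and means that Week 4 is not empty by construction; deleting the row would lose early deaths.

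**Regional distortion.** One could picture one region always scanned early and the other always late, showing 83% against 100% at Week 10 with identical disease. Nothing in the documents suggests such a split. A milder imbalance still registers. With 60% of scans early in one group and 40% in the other, Week 10 reads 1 − 0.6 × 0.168 = 89.9% against 1 − 0.4 × 0.168 = 93.3%. At Week 12, with S(9) = 0.832 and S(11) = 0.799, the readings are 81.9% and 81.2%.

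**Handled elsewhere.** The Kaplan-Meier curve is planned, the percentiles have intervals, and the row list is open-ended. Table 8.3.3 is a sensitivity analysis whose content the shells do not define. The supplied SAP text holds only reporting conventions and shells, so a rule in a methods narrative cannot be excluded. Appendix section 14.1.26 raises schedule bias as an optional sensitivity analysis; no supplied text adopts it. None of this puts an interval on the row rates.

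**Weight.** The study is descriptive with no hypothesis test (protocol section 10.7), so no formal decision rests on these rows. That limits the consequence but does not excuse the missing intervals.

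**Conclusion.** The point holds as one of presentation and precision. From Week 10, Table 8.3.1 and the tables sharing its layout read PFS at mid-window, so the rates depend on scan punctuality. Relative to underlying progression the shift was upward in every scenario run. Its central size, 10 points falling to 4 between Weeks 10 and 50, rests on the exponential curve, the borrowed 7.82-month median, uniform scan timing and no events outside scans, so it should be quoted only with its range.

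The missing interval needs no modelling. Section 10.2 promises 95% intervals for main estimators, the PFS rate is key secondary, and its companions ORR and CBR have intervals in Table 8.1.1. Section 10.2 does not list the main estimators, so the plan could be read as covering percentiles only; the key secondary status argues against that reading.

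A reader might extend the argument to time to response in Table 8.1.3. It does not carry over: the event there is response, and late dating makes the result look worse.

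**What to change.** In Tables 8.3.1 to 8.3.3 and S1 to S4.8.3.1:

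1. Add a pointwise two-sided 95% confidence interval to each event-free probability.
2. Read PFS at Weeks 12, 22, 32, 42 and 52, each labelled as the close of the corresponding scan window. The label matters: under the base assumptions these readings match underlying progression at the nominal week, and still exceed it at the stated week by 3.3 points (Week 12) down to 1.4 (Week 52).
3. Keep Week 4, with a footnote that no on-treatment scan is scheduled before it.

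Leave Table 8.1.3 unchanged on this argument.

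The cost is an edit to the shells and their programs; no new data are needed. The printed PFS rates become less favourable, and the rows no longer match the nominal visit weeks or the Week 20 and Week 50 response summaries.

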3.1.1 Primary endpoints

The primary endpoints are safety and tolerability evaluations, assessed according to the Common Terminology Criteria (CTCAE), version 4.03. This includes the incidence of adverse events (AEs) by grade, incidence of serious adverse events (SAEs), changes from baseline in vital signs, as well as changes from baseline in laboratory results (hematology, blood chemistry, lipid profile, viral markers) qualifying as AEs.

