Table 10.1.2 Vital Signs: Observed and Change from Baseline for Asian Patients- Safety Set

Asian: Indonesia, India, Vietnam, Turkey, South Korea, Thailand, Malaysia, Taiwan or Jordan.

SD: Standard Deviation.

Table 10.1.3 Vital Signs: Observed and Change from Baseline for Non-Asian Patients- Safety Set

Non-Asian: Australia, Morocco, South Africa or Tunisia.

SD: Standard Deviation.

These tables will be created using the same layout as Table 10.1.1.

Table 10.1.4 Vital Signs: Shift Table Based On Notable Values - Safety Set

Baseline	n (%)	Total (N=xxx)				
		Worst post-baseline value				
		Normal n (%)	High only n (%)	Low only n (%)	High and Low n (%)	Missing n (%)
Temperature (°C)						
Normal	xx (xx.x)	xx (xx.x)	xx (xx.x)	xx (xx.x)	xx (xx.x)	xx (xx.x)
High only	xx (xx.x)	xx (xx.x)	xx (xx.x)	xx (xx.x)	xx (xx.x)	xx (xx.x)
Low only	xx (xx.x)	xx (xx.x)	xx (xx.x)	xx (xx.x)	xx (xx.x)	xx (xx.x)
Missing	xx (xx.x)	xx (xx.x)	xx (xx.x)	xx (xx.x)	xx (xx.x)	xx (xx.x)
Total	xx (xx.x)	xx (xx.x)	xx (xx.x)	xx (xx.x)	xx (xx.x)	xx (xx.x)
Heart rate (bpm)						
Normal	xx (xx.x)	xx (xx.x)	xx (xx.x)	xx (xx.x)	xx (xx.x)	xx (xx.x)
High only	xx (xx.x)	xx (xx.x)	xx (xx.x)	xx (xx.x)	xx (xx.x)	xx (xx.x)
Low only	xx (xx.x)	xx (xx.x)	xx (xx.x)	xx (xx.x)	xx (xx.x)	xx (xx.x)
Missing	xx (xx.x)	xx (xx.x)	xx (xx.x)	xx (xx.x)	xx (xx.x)	xx (xx.x)
Total	xx (xx.x)	xx (xx.x)	xx (xx.x)	xx (xx.x)	xx (xx.x)	xx (xx.x)
SBP (mmHg)						
Normal	xx (xx.x)	xx (xx.x)	xx (xx.x)	xx (xx.x)	xx (xx.x)	xx (xx.x)
High only	xx (xx.x)	xx (xx.x)	xx (xx.x)	xx (xx.x)	xx (xx.x)	xx (xx.x)
Low only	xx (xx.x)	xx (xx.x)	xx (xx.x)	xx (xx.x)	xx (xx.x)	xx (xx.x)
Missing	xx (xx.x)	xx (xx.x)	xx (xx.x)	xx (xx.x)	xx (xx.x)	xx (xx.x)
Total	xx (xx.x)	xx (xx.x)	xx (xx.x)	xx (xx.x)	xx (xx.x)	xx (xx.x)
DBP (mmHg)						
Normal	xx (xx.x)	xx (xx.x)	xx (xx.x)	xx (xx.x)	xx (xx.x)	xx (xx.x)
High only	xx (xx.x)	xx (xx.x)	xx (xx.x)	xx (xx.x)	xx (xx.x)	xx (xx.x)
Low only	xx (xx.x)	xx (xx.x)	xx (xx.x)	xx (xx.x)	xx (xx.x)	xx (xx.x)
Missing	xx (xx.x)	xx (xx.x)	xx (xx.x)	xx (xx.x)	xx (xx.x)	xx (xx.x)
Total	xx (xx.x)	xx (xx.x)	xx (xx.x)	xx (xx.x)	xx (xx.x)	xx (xx.x)

- Notably abnormal vital signs:

- Systolic blood pressure [mmHg]: ≥ 180 mmHg/ ≤ 90 mmHg with increase/decrease from baseline of ≥ 20 mmHg
- Diastolic blood pressure [mmHg]: ≥ 105 mmHg/ ≤ 50 mmHg with increase/decrease from baseline of ≥ 15 mmHg
- Pulse rate [bpm]: ≥ 120 bpm/ ≤ 50 bpm with increase/decrease from baseline of ≥ 15 bpm

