- Temperature(°C): $\geq 39.1^\circ\text{C}$ or $\leq 35^\circ\text{C}$

- If a patient has both High and Low post baseline values then count in High and Low.
- Baseline is defined as the last non-missing value prior to the first study drug dose.
- Baseline percentage is based on N. Percentage for worst post-baseline value is based on Baseline n.

Table 10.1.5 Vital Signs: Shift Table Based On Notable Values for Asian Patients- Safety Set

Asian: Indonesia, India, Vietnam, Turkey, South Korea, Thailand, Malaysia, Taiwan or Jordan.

- Notably abnormal vital signs:

Systolic blood pressure [mmHg]: ≥ 180 mmHg/ ≤ 90 mmHg with increase/decrease from baseline of ≥ 20 mmHg

Diastolic blood pressure [mmHg]: ≥ 105 mmHg/ ≤ 50 mmHg with increase/decrease from baseline of ≥ 15 mmHg

Pulse rate [bpm]: ≥ 120 bpm/ ≤ 50 bpm with increase/decrease from baseline of ≥ 15 bpm

Temperature($^{\circ}$ C): $\geq 39.1^{\circ}$ C or $\leq 35^{\circ}$ C

- If a patient has both High and Low post baseline values then count in High and Low.

- Baseline is defined as the last non-missing value prior to the first study drug dose.

- Baseline percentage is based on N. Percentage for worst post-baseline value is based on Baseline n.

Table 10.1.6 Vital Signs: Shift Table Based On Notable Values for Non-Asian Patients- Safety Set

Non-Asian: Australia, Morocco, South Africa or Tunisia.

- Notably abnormal vital signs:

Systolic blood pressure [mmHg]: ≥ 180 mmHg/ ≤ 90 mmHg with increase/decrease from baseline of ≥ 20 mmHg

Diastolic blood pressure [mmHg]: ≥ 105 mmHg/ ≤ 50 mmHg with increase/decrease from baseline of ≥ 15 mmHg

Pulse rate [bpm]: ≥ 120 bpm/ ≤ 50 bpm with increase/decrease from baseline of ≥ 15 bpm

Temperature($^{\circ}$ C): $\geq 39.1^{\circ}$ C or $\leq 35^{\circ}$ C

- If a patient has both High and Low post baseline values then count in High and Low.

- Baseline is defined as the last non-missing value prior to the first study drug dose.

- Baseline percentage is based on N. Percentage for worst post-baseline value is based on Baseline n.

These tables will be created using the same layout as Table 10.1.4.

Table 10.2.1 Local Hematology Data: Change from Baseline Overall and in Asian Subgroup - Safety Set

Laboratory Test/ Visit	Statistic	Asian (N=xx)	Non-Asian (N=xx)	Total (N=xxx)
Complete Blood Count (CBC): Baseline (BL)	Observed, n	xx	xx	xx
	Mean (SD)	xx (xx.x)	xx (xx.x)	xx (xx.x)
	Median	xx	xx	xx
	Min, Max	xx.x, xx.x	xx.x, xx.x	xx.x, xx.x

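### The vital-sign shift tables define High and Low by a limit plus a change from baseline, so baseline blood pressure and pulse can never be High or Low and many out-of-limit values are tabulated as Normal

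*SAP*

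**What the plan says.** Table 10.1.4 in SAP section 1.2 is titled "Vital Signs: Shift Table Based On Notable Values - Safety Set". Tables 10.1.5 and 10.1.6 repeat it for Asian and non-Asian patients with the same footnotes. For temperature, heart rate, systolic pressure (SBP) and diastolic pressure (DBP), the rows give the baseline category (Normal, High only, Low only, Missing). The columns give the worst post-baseline category.

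High and Low are defined only in the footnote on notably abnormal values:

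- SBP: "Systolic blood pressure [mmHg]: ≥ 180 mmHg/ ≤ 90 mmHg with increase/decrease from baseline of ≥ 20 mmHg"
- DBP: "Diastolic blood pressure [mmHg]: ≥ 105 mmHg/ ≤ 50 mmHg with increase/decrease from baseline of ≥ 15 mmHg"
- Pulse: "Pulse rate [bpm]: ≥ 120 bpm/ ≤ 50 bpm with increase/decrease from baseline of ≥ 15 bpm"

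Temperature has absolute limits only (39.1 °C and 35 °C), with no change component.

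Two further footnotes matter. "Baseline is defined as the last non-missing value prior to the first study drug dose", so each patient has one baseline value. "Percentage for worst post-baseline value is based on Baseline n", so the baseline category sets the denominator of every shift percentage.

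The protocol's primary endpoints (section 3.1.1) include "changes from baseline in vital signs". Section 10.5 adds that notable values will be flagged, and describes the safety analysis as descriptive.

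**The concern.** A shift table is read by comparing a patient's category before treatment with her worst category on treatment. That works only if the same scale applies at both times. Here the scale for blood pressure and pulse contains a change from baseline, which has no meaning at baseline itself. The shell nevertheless prints baseline rows for High only and Low only.

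The laboratory shift tables in the same SAP do not have this problem. Tables 10.2.2 and 10.3.2 use CTC grade, and Tables 10.2.5 and 10.3.5 use the normal range, each on one absolute scale at baseline and afterwards.

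At stake is the reading of one component of the primary safety endpoint. Patients with out-of-limit blood pressure or pulse would sit in a cell labelled Normal. The protocol's background section lists hypertension among the most common grade 3/4 drug reactions. The eligibility criteria set no numeric blood pressure limit, so out-of-limit baselines are not ruled out by number.

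**Working it through.** The plan gives no figure to reproduce. The check applies the footnote literally and compares it with the absolute limits alone.

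**Inputs** (footnote to SAP Table 10.1.4), for baseline b and later value v:

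| Parameter | High if | Low if |
|---|---|---|
| SBP | v ≥ 180 and v − b ≥ 20 | v ≤ 90 and b − v ≥ 20 |
| DBP | v ≥ 105 and v − b ≥ 15 | v ≤ 50 and b − v ≥ 15 |
| Pulse | v ≥ 120 and v − b ≥ 15 | v ≤ 50 and b − v ≥ 15 |

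**Step 1: baseline rows.** At baseline v = b, so the change is 0, which is below 15 and 20. Applying the rule to every whole number from 20 to 260 for each parameter gives Normal every time. Two rows (High only, Low only) for three parameters, 2 × 3 = 6 rows per table, can never be filled.

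**Step 2: post-baseline SBP.**

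| Baseline → later (mmHg) | Change | Footnote, literal | Absolute limits at both times |
|---|---|---|---|
| 185 → 185 | 0 | Normal → Normal | High → High |
| 185 → 190 | +5 | Normal → Normal | High → High |
| 185 → 204 | +19 | Normal → Normal | High → High |
| 185 → 205 | +20 | Normal → High | High → High |
| 180 → 199 | +19 | Normal → Normal | High → High |
| 180 → 200 | +20 | Normal → High | High → High |
| 165 → 184 | +19 | Normal → Normal | Normal → High |
| 160 → 180 | +20 | Normal → High | Normal → High |
| 95 → 85 | −10 | Normal → Normal | Normal → Low |
| 85 → 85 | 0 | Normal → Normal | Low → Low |
| 110 → 90 | −20 | Normal → Low | Normal → Low |

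Two groups are therefore shown as Normal post-baseline despite an out-of-limit value. One is patients already beyond a limit who do not move far enough further in the same direction. The other is patients who cross a limit by a small change. The same holds for DBP and pulse with a margin of 15: DBP 110 → 124 is a rise of 14, hence Normal, and 110 → 125 is a rise of 15, hence High.

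**Step 3: a mixed reading.** Suppose a programmer fills the empty rows by applying the limit alone at baseline but keeps the footnote afterwards. Then 185 → 195 is High at baseline (185 ≥ 180) and Normal later (195 − 185 = 10, below 20). The table shows High → Normal, an apparent improvement in a patient whose pressure rose. The SAP does not state this rule.

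**Step 4: missing baseline.** No change can be computed, so a patient in the Missing row cannot be High or Low for blood pressure or pulse, whatever her later values.

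**Step 5: the listings.** The example flags in Listings 16.1 and 16.2 show SBP below 90 mmHg and pulse above 90 bpm on the Screening row. They have no change component, and the pulse limit differs from the 120 bpm in the table. They may be placeholders, but they do not match the footnote.

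**The case against.** The best defence is that the criterion is meant to pick out values that are both extreme and materially changed from the patient's own baseline. The endpoint is change in vital signs, and a stable 185 mmHg has not changed. On that view the post-baseline columns work as a count of newly notable values. The empty rows and the label Normal are then faults of presentation. This stands in part: the limit-plus-change count is useful and should be kept. It does not rescue the baseline rows, and it does not make Normal a fair label for 185 mmHg.

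Three stronger inferences are tempting, and the documents do not support them:

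- *Anyone who stays at or above 180 mmHg is shown as Normal.* Not so: with a later value at least 20 mmHg above her baseline she is High, as 185 → 205 shows.
- *The table will show false improvement.* That needs the unwritten limit-only rule at baseline. The printed rows hint at such a rule, but no text states it.
- *Persistent abnormal values are hidden from the safety evaluation.* Tables 10.1.1 to 10.1.3 give observed values and changes at each visit, with minimum and maximum. Listing 16.1 shows each patient's values by visit. Protocol section 7.2.2 sends findings compatible with adverse events to the adverse event form, and section 10.5 rests the safety assessment mainly on adverse event frequency.

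**Conclusion.** The point holds as a minor display error. Read literally, the footnote leaves six baseline rows in each of the three tables empty by construction. It also tabulates as Normal any out-of-limit SBP, DBP or pulse that has not moved from baseline by the required 20 mmHg, 15 mmHg or 15 bpm in the direction of that limit. This is a consequence of the written rule and does not depend on the data.

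The number of patients affected cannot be derived from the documents and may be small. Temperature is not affected. The analysis is descriptive, and the underlying values are reported elsewhere, so no safety conclusion need be wrong because of it.

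The conclusion assumes that the footnote is the only rule. The public SAP text consists of reporting conventions and output shells, so a rule for classifying baseline in a part not included there cannot be excluded.

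**What to change.** In Tables 10.1.4 to 10.1.6:

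1. Classify both the baseline and the worst post-baseline value by the absolute limits already in the footnote: SBP 180 and 90 mmHg, DBP 105 and 50 mmHg, pulse 120 and 50 bpm. Leave temperature as it is.
2. Report the limit-plus-change criterion as a separate count of newly notable values, for patients with a baseline and at least one later value. This keeps the filter against small crossings such as 165 → 184.
3. Make the flags in Listings 16.1 and 16.2 use the same limits, and say which of the two definitions each flag represents.

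A lighter change would state a baseline rule and rename Normal as not notable. That would settle the ambiguity. But if the rule were limit-only at baseline, the two time points would still be on different scales, and 185 → 195 would still appear to improve.

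The cost is one footnote, one derived flag and one extra count. No new data are needed and no existing information is lost.
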